Enrollment began in April 2016 in North Carolina and June 2016 in New York and will end in the fall 2017 for both locations. Baseline data collection began in August 2016 and will end in fall 2017. The 12-month follow-up data collection will occur in fall 2017 for youth who enrolled during the 2016-17 school year.

Prepared for the Office of Adolescent Health by Mathematica Policy Research under contract #GS-10F-0050L, Task Order No. HHSP233201300416G with Center for Supportive Schools with grant #6 TP2AH000037.

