- a.* **Sample formation:** Participants were enrolled during the 2016-2017 (Cohort 1) and 2017-2018 (Cohort 2) school year. Cohort 1 participants were recruited from two high schools in North Carolina and four in New York; Cohort 2 participants were recruited from nine high schools in North Carolina and six in New York. Participants were recruited from three of the same New York schools during both the 2016-2017 and 2017-2018 school years; thus, a total of 18 schools are participating in the study (11 from North Carolina and 7 from New York).

Potential study participants were identified through a consent/assent and eligibility screening process. Parental consent and student assent forms asked students and parents to confirm whether the student was planning to attend ninth grade at a participating study school during the upcoming academic year and to review and sign the form, indicating whether they agreed for the student to participate in the study. Consent/assent procedures differed depending on whether the school was located in North Carolina or New York. Within North Carolina, in the spring prior to enrollment at a study school, eighth grade students who attended feeder middle schools received copies of the parental consent and student assent forms in their homeroom classrooms. For some schools, where randomization was scheduled to take place several weeks into students' ninth grade year, additional forms were passed out to students in their freshman homeroom classes in the fall. Within New York, where a clear system of feeder middle schools does not exist, ninth grade students were not contacted until after they enrolled in (began) high school. Parental consent and student assent materials were distributed during the first two weeks of the school year and students were asked to return the signed forms to school by a specific date. In both locations, additional opportunities to recruit rising ninth grade students included high school orientation events held in the spring or summer before students' ninth grade year and via communication methods that were approved by school administration, such as postcards that shared instructions on how to consent using an online version of the consent form or mailing consent packets directly to students and parents.

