- ii.* **Random assignment procedure:** Random assignment was conducted prior to the administration of the baseline *Participant Questionnaire* at each school. A lead research analyst used an existing algorithm available in Stata (random allocation command, *ralloc*) to generate a list of random assignments based on the total number of students who met eligibility criteria and were enrolled in the study. The list of eligible and enrolled students was alphabetized by last and then first name. The alphabetized student list was then paired with the random assignment list. This is when random assignment occurred – when a student name was associated with a treatment condition. Random assignment blocks of varying sizes assigned participants to the treatment or control condition at an equal (i.e., 1:1) assignment ratio within each participating school. The allocation lists are password-protected and stored on a secure PRG server and were also shared with each individual school so that administrators could ensure that students assigned to the treatment condition were pulled out of class during each *PGC* outreach session to receive the intervention.

The research analyst for the study prepared a *Study Roster* for each school, which listed the full name of each student, the condition to which the student was assigned, and associated a unique five-digit study ID with each student.

For both baseline and follow-up data collection, the study team prepares paper questionnaires pre-printed with each unique study ID number and organizes them according to school. During questionnaire administration, the study team ensures that each individual student receives the instrument with his or her assigned unique ID number. This number is associated with the participant's questionnaire data.²

- iii. **Blocking procedures:** Blocking occurs at the school level. Participants are enrolled and randomized at the individual level within each participating study school.
 - iv. **Probability of assignment to treatment group:** The probability of assignment to the treatment group is intended to be equal to the probability of assignment to the control condition; that is, p (assignment to treatment) = .5.

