- c) Race – race of participant as self-reported at baseline. Race will be coded as a set of 4-1 = 3 dummy variables (each coded as 1 if they are of the specified race and coded as 0 otherwise); each of the variables will be re-centered at the grand mean for analysis.
- d) Hispanic/Latino – self-reported as Hispanic, Latino, or of Spanish origin at baseline (0=do not identify as Hispanic/Latino/Spanish origin; 1=identify as Hispanic, Latino, of Spanish origin); variable will be re-centered at the grand mean for analysis.
- e) School – An $n-1$ vector of school indicator dummy variables that are coded one if the intervention was delivered at school n and coded zero otherwise. School 1 is the reference category and is excluded from analysis. The dummy variables will be mean-centered for analysis to facilitate interpretation.

β_0 – The intercept term, which represents, depending on the outcome measure of interest in the analysis, the outcome for the average control participant with all other variables in the model held constant at their mean.

β_1 – This is the parameter estimate of substantive interest. β_1 represents, depending on the outcome measure of interest in the analysis, either: 1) the adjusted mean difference in treatment and control participants’ self-reported sexual initiation at the 10th follow-up; 2) the adjusted mean difference in treatment and control participants’ self-reported times having sex in the past three months at the 10th grade follow-up; or 3) the adjusted mean difference in treatment and control participants’ self-reported number of sexual partners in the past three months at the 10th follow-up.

ε – The error term or unexplained individual-level variance that remains for each observation after the structural components of the model are estimated. It is the difference between the observed and the predicted values at the individual level.

We will report model-estimated effects and the results of significance tests in the findings section of the final impact report. Statistical significance will be based on test statistics produced by Stata for the coefficient β_1 using a two-tailed test, with $p < .05$.

- ii. **Sample attrition:** Overall and differential attrition will be calculated using the full sample of students enrolled in the study. This will be determined using data within the *Questionnaire Completion Database*. We will calculate overall attrition using the following formula:

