Hispanic, Latino or of Spanish origin	
The measure is operationalized as a dummy variable, where 0 = identify as another ethnicity/do not identify ethnicity; 1 = identify as Hispanic, Latino or of Spanish origin.
 
The measure is taken from the following item on the baseline Participant Questionnaire:
	
Research has shown that Black/African American and Hispanic adolescents are more likely to engage in sex during adolescence and initiate sexual activity at a younger age (Blum 2000; Brewster 1999; Hogan et al 2000; Kirby 2007; Scott Jones and White 1990)

Covariate	Description of the covariate and how it will be used as a covariate in the analysis	Rationale for inclusion
	
 • What is your race? (Participants can select more than one response) 
 ○ White ○ Black or African American ○ Hispanic, Latino, or of Spanish origin ○ American Indian or Alaska Native ○ Asian ○ Native Hawaiian or Pacific Islander ○ Some other race (specify) 
Variable will be coded as 1 if participant self-identified as Hispanic, Latino or of Spanish origin, regardless as to whether other races/ethnicities are specified; Hispanic, Latino or of Spanish origin is not selected, the response will be coded as 0.
	
Blocking Covariates		
School	
The measure is operationalized a set of $n-1$ dummy variables, where n refers to the number of participating schools over the course of the evaluation period.
 
Data for the measure are obtained from the Randomization dataset.
 
Each dummy will be coded as 1 if the individual is enrolled in a particular school and 0 otherwise. School 1 is the reference variable. Dummy variables will be grand mean centered so that the intercept will then reflect the un-weighted mean site effect.
	Randomization is blocked by school.

Table 3: Data Editing Rules

The following table provides PRG's general rules for editing data based upon responses given.

Category	Data editing rule
No response given to an item (coded as .f)	If data from a related variable can be used to infer a value, data will be logically edited. Otherwise, the value will be left as missing.
Invalid items (coded as .i)	Adjust missing baseline values
Outlying items (Outlier indicator variable coded as 1)	Keep in benchmark analysis; run sensitivity analyses excluding outliers

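### Three New York schools appear to have been randomised in two separate years, but the models adjust for school only, so the blocking covariate is slightly coarser than the randomisation

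*Combined protocol and SAP*

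**What the plan says.** Section 3a describes two enrolment years: "Participants were enrolled during the 2016-2017 (Cohort 1) and 2017-2018 (Cohort 2) school year". On the schools it says "Cohort 1 participants were recruited from two high schools in North Carolina and four in New York" and "Cohort 2 participants were recruited from nine high schools in North Carolina and six in New York". It adds that "Participants were recruited from three of the same New York schools during both the 2016-2017 and 2017-2018 school years", and so "a total of 18 schools are participating in the study".

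Section 3b.ii gives the timing: "Random assignment was conducted prior to the administration of the baseline" questionnaire at each school. The assignment list was sized to the students already found eligible and enrolled. Their names were put in alphabetical order and paired with the assignments, in blocks of varying size at 1:1 within school. Section 3b.iii places blocking at the level of the school and does not mention cohort. Section 3b.iv gives an assignment probability of .5.

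In the impact model (4f.i, item e) the blocking term is a "vector of school indicator dummy variables that are coded one if the intervention was delivered at school" n, with School 1 as reference. Table 2 defines n for these dummies: "n refers to the number of participating schools over the course of the evaluation period". The baseline-equivalence model (4d, step 1) uses the same school vector. No cohort or school-by-cohort term appears in either model, in Table 2 or in the sensitivity analyses of 4f.iv.

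**The concern.** The plan includes school dummies because randomisation was blocked by school, so the covariate is meant to mirror the groups within which students were assigned. For 15 of the 18 schools it does. In the three schools used in both years, students entering in 2017-18 cannot have been on a list built and used before the 2016-17 baseline. Each of these schools therefore seems to hold two independently randomised groups, which the model treats as one.

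Two things are at stake, both small. Any difference in outcome between the two year-groups of a repeat school stays in the residual and costs precision. And if the treated share among analysed students differs between the two years, by chance or because follow-up differed by arm and year, part of the year difference is carried into the treatment coefficient without adjustment.

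**Working it through.** **Count of schools and groups (inputs from section 3a).**
- Cohort 1: 2 + 4 = 6 schools. Cohort 2: 9 + 6 = 15 schools.
- Distinct schools: 6 + 15 - 3 = 18 (North Carolina 2 + 9 = 11; New York 4 + 6 - 3 = 7). This reproduces the plan's own figure of 18.
- School-by-cohort groups: 6 + 15 = 21.
- Dummies in the plan: 18 - 1 = 17. Dummies for the groups: 21 - 1 = 20. The difference of three is one for each repeat school.

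**Precision, sexual initiation.** The documents give no outcome rates, group sizes or cohort differences, so these are assumptions: 6 of 21 equal-sized groups lie in the repeat schools, the initiation rate is 25% (variance 0.25 × 0.75 = 0.1875), and the year-groups differ by δ. Two equal groups that differ by δ contribute a between-group variance of δ²/4.

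Share of residual variance = (6/21) × (δ²/4) / 0.1875. The effect on the standard error is about half that share.

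| δ | share of residual variance | effect on SE |
|---|---|---|
| 0.05 | 0.10% | 0.05% |
| 0.10 | 0.38% | 0.19% |
| 0.15 | 0.86% | 0.43% |

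**Unadjusted difference in treated share.** If the treated share in the repeat schools differs by d between the two years, in the same direction in all three and averaging one half, the treatment coefficient shifts by about (6/21) × δ × d.
- δ = 0.05, d = 0.05: 0.07 percentage points.
- δ = 0.10, d = 0.05: 0.14 percentage points.
- δ = 0.15, d = 0.10: 0.43 percentage points.

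The values of d are also assumptions.

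**Simulation check.** Permuted-block 1:1 assignment was simulated in 21 equal groups (assumed block sizes 2, 4 and 6), with a 25% rate, no treatment effect and 2,000 runs per setting. The total sample was about 1,200 or 1,600; 1,600 is the expected enrolment in the Evaluation Abstract. The assumed cohort difference was 0, 10 or 20 points. OLS was fitted with 18 school effects and with 21 group effects.
- The mean treatment estimate was within 0.0007 of zero under both models.
- Type I error differed between the models by at most 0.3 points.
- At 1,600 and a 20-point difference, the mean SE was 0.02170 with 18 effects and 0.02153 with 21; 0.02170 / 0.02153 = 1.008, about 0.8% larger. The formula above gives the same at δ = 0.20: (6/21) × 0.01 / 0.1875 = 1.5% of the variance, or about 0.8% of the SE.
- With no cohort difference the SEs were the same.

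**The case against.** The plan is consistent with its own description. Section 3b.iii says blocking is by school, Table 2 gives that as the reason for the school dummies, and no sentence mentions lists by cohort or the number 21. A reader might infer that the documents state 21 lists and that the analysis contradicts them. They do not: 21 is a deduction from the enrolment years in 3a and the list-building procedure in 3b.ii. The deduction is sound, but it should be checked against the records.

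A reader might also infer that the treatment estimate is biased or the test invalid. The documents do not support that. Assignment probability is .5 everywhere, so within a repeat school treatment is unrelated to cohort by design. Chance imbalance between years is already reflected in the standard error, which is if anything slightly conservative. The largest shift shown, 0.43 points, compares with a simulated SE of about 2.2 points at 1,600 students.

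Three further points stand. The model already adjusts for the baseline outcome, age, gender, race and ethnicity, which would absorb part of any year difference present at entry, so the gain may be smaller than shown. Attrition that differs by year but equally in both arms does not change the treated share, and group dummies cannot remove attrition bias within a group. And strict conditioning on the randomisation would mean the small blocks inside each list. Adjusting at the level of the list is a convention, so this is a matter of degree.

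What survives is that the plan chose to adjust for its blocking groups and defined them too coarsely in three schools, where the finer definition is available at no cost.

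**Conclusion.** The point holds as a minor, free improvement. The documents imply 21 randomisation groups and the models adjust for 18 schools; the gap is confined to the three New York schools enrolled in both years. Validity is not in question. For sexual initiation the cost is an SE about 0.05% to 0.4% too large, plus an unadjusted shift of roughly 0.1 to 0.4 percentage points if treated shares differ between years. These sizes rest on the assumed 25% rate, equal group sizes, cohort differences of 5 to 15 points and share differences of 5 to 10 points. No comparable figure can be given for the two count outcomes, because the documents give no means or variances for them. Nothing here would be expected to change a conclusion of the trial.

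**What to change.** First confirm from the Randomization dataset that the three repeat schools were assigned separately in each year, and that there are 21 groups in all. Then, in 4f.i item e, 4d step 1 and Table 2, define the blocking covariate as the school-by-cohort randomisation group: 20 dummies for 21 groups, mean-centred in 4f.i as now. One sentence in 3b.iii should say that blocking was by school within cohort.

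The cost is a short edit and three more parameters, against an expected enrolment of about 1,600. No new data are needed, since school already comes from the Randomization dataset and enrolment year is known. If cohort is left out on purpose, the plan should say so, so that the choice is not made after results are seen.
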